10.4.2 Statistical hypothesis, model, and method of analysis

No hypotheses or models will be considered for these analyses and descriptive statistics will be provided; inferences to the target population (when applicable) will be made using interval estimation.

The proportion of patients who reach the overall response rate (partial and complete) by 16 weeks after the initiation of eltrombopag will be calculated and the corresponding 95% confidence interval (CI). This CI will be one-sided and will be constructed using the relationship between the sums of binomial probabilities and the F distribution described by Clopper and Pearson using the formulas proposed elsewhere (Fleiss JL, Levin B, Paik MC. Statistical Methods for Rates and Proportions. Third edition. John Wiley & Sons: New York, 2003, pp. 25):

$$P_L = \frac{x_0}{x_0 + (n - x_0 + 1)F_{2(n-x_0+1), 2x_0; \alpha}}$$

where $\alpha=0.05$, x_0 is the observed number of responders in the sample and n the sample size.

Descriptive statistics will also be provided between baseline and 16 weeks for blood cell counts (ANC and platelet) and hemoglobin levels, and appropriate paired exploratory tests will be done according to the type of distribution (parametric or not) to assess the statistical significance of the changes.

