6.3.1 Permitted concomitant therapy

6.3.1.1 Supportive care

Granulocyte colony-stimulating factor (G-CSF) and erythropoietin (EPO) therapies are permitted.

Transfusions for platelets and/or RBC may be given, as medically needed.

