7.2.1.1 Eligibility screening

Patients must meet all inclusion and exclusion criteria at Screening to be eligible to proceed to the treatment period of the study.

The platelet count needs to be <20,000/ μ L (mandatory) along with the ANC <1,000/ μ L and/or hemoglobin <100 g/L in a peripheral blood analysis on day +30 or beyond after allo-HSCT to qualify the patient for enrolment. Platelets, ANC and hemoglobin re-tests in a peripheral blood analysis will be required at Screening within 7 days prior to intended study Day 1, to allow sample time for results to be returned before administration of eltrombopag.

Patient eligibility will be confirmed by the investigative staff and captured within the source documents maintained at the site. This information will be made available during planned interim monitoring visits and compared against the clinical database for accuracy. Only when eligibility has been confirmed will the patient initiate the study treatment. Additionally, investigative site staff will enter patient information into the electronic case report form (eCRF), and automated queries will be generated for immediate resolution should patient eligibility be in question based on the patient information entered.

Re-screening of a previously screen failed patient will be allowed only once. A patient may be re-screened once if there are exclusionary medical condition at the Screening that may resolve and allow for re-screening. Some examples of re-screening reasons are listed below. In cases of re-screening, eligibility must be confirmed with Novartis.

- Laboratory value(s) out of range due to sampling error or that might be within range after medically-appropriate supplementation. (Note: Before screen failing and then re-screening the subject, efforts should be made to repeat the laboratory assessment(s) during the original initial screening phase).
- Vital signs and ECG abnormalities that can be stabilized.
- The patient has a medical condition that can be stabilized or resolved prior to the repeat screening attempt.

Patients who are rescreened must sign a new informed consent and they will be assigned with a new patient identification number. All required screening activities must be performed when the patient is rescreened for participation in the study.

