7.2.2 Treatment Period

All patients included in the study will be treated with eltrombopag up to week 36 or until the patient's premature withdrawal (see [Sections 6.1.2/7.2.3.1](#)) (Final visit [or Early withdrawal]).

- Only patients who respond at week 16 will continue to receive eltrombopag until loss of response (i.e. declining blood counts that do not continue to meet the criteria for response established in this protocol), unacceptable toxicity, or discontinuation for any other reason (see [Sections 6.1.2/7.2.3.1](#))
- Patients who discontinue eltrombopag because efficacy (See [Section 6.1.2](#)), will continue in the study and attend the scheduled visits as per protocol. If loss of response occurs, eltrombopag will be reintroduced at the last effective dose (See [Section 6.1.2](#))

During the treatment period, patients will be evaluated weekly during the first month, every 2 weeks during the next 2 months and subsequently every 4 weeks until week 24. For the last 3 months, patients will be followed every 6 weeks.

7.2.2.1 Day 1

The Day 1 visit may occur as soon as all screening /baseline evaluations have been completed, and all results are available prior to the first dose of eltrombopag. The following procedures will be performed and all observations will be recorded in the eCRF:

- Supportive care (see [Section 6.3.1.1 / 7.3.1.2](#))
- Physical examination (See [Section 7.3.2.1](#))
- Weight (See [Section 7.3.2.3](#))
- Vital signs (See [Section 7.3.2.4](#))
- Dispense study drug for the first 7 days:
 - The importance of compliance will be reviewed with the patient.
 - The patient will be educated on medications and food that should be avoided while taking eltrombopag.
- Record concomitant medication (See [Section 6.3](#)).
- Patients will be instructed to call the investigator or designated research staff if they experience any unexpected and unfavorable signs and/or symptoms (See [Section 8.1](#)). These adverse events will be recorded on the eCRF.

NOTE: Hematology and biochemistry will not need to be repeated at Day 1 as they should have been performed at the screening period (in the 7 days prior to start study treatment).

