10.5.1 Other efficacy objective(s)

- To determine the response in each haematological lineage separately, the absolute frequency and valid percentage of patients who have a response in the neutrophil, platelet, and Hb lineages separately after 16, 24 and 36 weeks of eltrombopag, will be presented with the 95% CI. Descriptive statistics will also be provided between baseline and weeks 16, 24 and 36 for ANC, platelets and hemoglobin levels, and the appropriate paired exploratory tests will be done according to the type of distribution (parametric or not) to assess the statistical significance of the changes.
- To evaluate the overall hematological response rate (partial and complete) at 24 and 36 weeks after the initiation of eltrombopag, the frequency and percentage distribution and the corresponding 95% CI will be provided. This CI will be constructed as for the primary efficacy endpoint. Descriptive statistics will also be provided between baseline and week 24 and week 36 for ANC, platelets count and hemoglobin levels, and the appropriate paired exploratory tests will be done according to the type of distribution (parametric or not) to assess the statistical significance of the changes.
- To evaluate transfusion independence, the percentage of patients who were previously transfusion-dependent and do no longer require a RBC or platelet transfusion before and after the first 16 weeks of treatment will be calculated along with the 95% CI. This CI will be constructed as for the primary efficacy endpoint. The period where patients did not receive any platelet or RBC transfusions during the treatment period and follow-up will also be analyzed.

- To evaluate the discontinuation or reduction of concomitant G-CSF and/or EPO therapy, the percentage of patients who discontinue or reduce by $\geq 50\%$ from baseline the use of concomitant G-CSF and/or EPO therapy will be calculated along with the 95% CI. This CI will be constructed as for the primary efficacy endpoint.
- Overall survival, defined as the duration from inclusion in the study to date of death (whatever the cause), will be estimated with the Kaplan-Meier curves method and two-sided 95% CI for the estimated median. All patients who discontinue from the study, regardless the reason of discontinuation, will be followed for survival for 24 and 36 weeks, unless they withdraw their consent, die or are lost-to follow-up, in which case will be censored at the last contact.

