### **3 STATISTICAL METHODS**

Quantitative variables are described with measures of central tendency and dispersion: mean, median, SD, Q1, Q3, minimum and maximum).

Qualitative variables are described using absolute and relative frequencies (N, %). Two percentage columns are presented, total percentage (total %) and valid percentage (valid %), that is, the percentage over the sum of valid responses plus missing values and the percentage over the total of valid responses. When there are not missing values both of them are equal, and then only one will be show.

[figure not shown]
In the analysis of contingency tables as well as for the comparison of proportions and / or frequency distributions, the chi-square test (or Fisher's exact when appropriate) will be used.

For dependent samples, parametric (t-test paired) or non-parametric (Wilcoxon) statistical tests will be performed depending on the distribution of the sample.

The "time to event" variables (overall survival) will be analyzed using the Kaplan-Meier method.

These tests will be used in all bilateral cases and with a level of significance of 0.05. In cases where a p-value less than 0.05 appears, it refers to the existence of statistical significance.

Data will be analyzed using SPSS v22.0.

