- To assess if there are statistical significance differences in ANC between baseline and week 36, it will be applied the appropriate paired test (T-test paired or Wilcoxon, depending the distribution of sample).
- To assess if there are statistical significance differences in platelets between baseline and week 24, it will be applied the appropriate paired test (T-test paired or Wilcoxon, depending the distribution of sample).
- To assess if there are statistical significance differences in platelets between baseline and week 36, it will be applied the appropriate paired test (T-test paired or Wilcoxon, depending the distribution of sample).
- To assess if there are statistical significance differences in hemoglobin between baseline and week 24, it will be applied the appropriate paired test (T-test paired or Wilcoxon, depending the distribution of sample).
- To assess if there are statistical significance differences in hemoglobin between baseline and week 36, it will be applied the appropriate paired test (T-test paired or Wilcoxon, depending the distribution of sample).

### 10.3 Secondary objective 2

**To evaluate the long-term efficacy of eltrombopag on overall hematologic response (partial and complete) at 24 and 36 weeks after the initiation of eltrombopag.**

It will be calculated:

- Percentage of patients who have secondary overall hematological response at 24 weeks, defined as the maintenance of a partial or complete response at 24 weeks.
- Percentage of patients who have secondary overall hematological response at 36 weeks, defined as the maintenance of a partial or complete response at 36 weeks.

[figure not shown]
### 10.4 Secondary objective 3

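### The exploratory paired tests against baseline use raw counts with no transfusion condition; for platelets, the <20,000 entry cap tilts them towards a false significant rise

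*Protocol*

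**What the plan says.** Protocol 10.4.2 adds to the primary analysis a comparison "between baseline and 16 weeks for blood cell counts (ANC and platelet) and hemoglobin levels, and appropriate paired exploratory tests will be done". Protocol 10.5.1 repeats it for the secondary objectives: "Descriptive statistics will also be provided between baseline and weeks 16, 24 and 36 for ANC, platelets and hemoglobin levels", again with paired tests. SAP 10.2 lists the tests at weeks 24 and 36 only, for example "To assess if there are statistical significance differences in platelets between baseline and week 24, it will be applied the appropriate paired test". SAP 3 sets the method ("For dependent samples, parametric (t-test paired) or non-parametric (Wilcoxon) statistical tests will be performed depending on the distribution of the sample") and the level ("These tests will be used in all bilateral cases and with a level of significance of 0.05").

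Four other provisions matter:

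- **Transfusion is allowed on study.** Protocol 6.3.1.1: "Transfusions for platelets and/or RBC may be given, as medically needed".
- **The platelet baseline is selected.** Inclusion criterion 3 makes a platelet count below 20,000/µL mandatory, and Protocol 7.2.1.1 says "Platelets, ANC and hemoglobin re-tests in a peripheral blood analysis will be required at Screening within 7 days prior to intended study Day 1". The Day 1 visit adds "NOTE: Hematology and biochemistry will not need to be repeated at Day 1", so the qualifying count is in effect the baseline.
- **The response definition is protected, the paired tests are not.** Partial response in platelets and in hemoglobin requires transfusion independence (Protocol 7.3.1.1 and 10.4.1). The paired tests carry no such condition.
- **There is no control arm** (Protocol 6.4.2).

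**The concern.** A platelet count lifted to 20,000/µL or more by donor platelets cannot be a baseline value, but it can be a week 16, 24 or 36 value. The same holds for a count that is high by chance. Even if transfusion use is identical at both times and the drug does nothing, the expected change is upward. No comparator group shares the bias and cancels it.

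At weeks 24 and 36 the problem can persist. A patient may stay on study through a neutrophil or hemoglobin response alone and still receive platelets. Withdrawal of patients without a response at week 16 (Protocol 6.1.2) adds a further upward selection.

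For hemoglobin, entry below 100 g/L is not mandatory, so a transfused value can sit on either side of the comparison. The change then partly reflects transfusion practice, and a real gain in a patient who stops needing red cells can be hidden.

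At stake is a misleading p-value in a single-arm efficacy report. SAP 3 treats p<0.05 as statistical significance, and the SAP text on these tests does not repeat the protocol's exploratory label.

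**Working it through.** **1. Inputs from the documents.** The plan gives no figure for the paired tests. The sample size does reproduce. With x = 0.45 × 33 = 14.85 and n = 33, the formula in Protocol 10.4.2 gives P_L = 14.85 / (14.85 + 19.15·F) = 0.3008, where F is the upper 5% point on 38.3 and 29.7 degrees of freedom. This matches the stated 30.1%. So n = 33 for week 16. At the planned 45% response about 15 patients remain at weeks 24 and 36. A two-sided 0.05 test allows 2.5% false rises.

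**2. Mechanism.** Take a patient with stable mean m. Baseline B = m·e₀ + T₀·I₀ is accepted only if B < 20,000. Follow-up is W = m·e₁ + T₁·I₁ with no limit. Here e is within-patient variation, T marks a transfused count and I is the residual increment. Without the entry rule B and W have the same distribution; a run with 50% transfused at both times and no entry rule gave 1.7% false rises. With the rule, high values are removed from B only, so the mean of W − B is positive. For example, m = 12,000 and I = 15,000 gives 27,000: impossible as a baseline, possible at follow-up, a change of +15,000 in a patient whose own count is unchanged.

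**3. Size, main model.** Assumptions not in the documents: patient means uniform 5,000-18,000; within-patient log SD 0.25; increments uniform 5,000-15,000 (low end of each range) or 10,000-30,000 (high end); the same transfused share at both times; no drug effect. Two-sided Wilcoxon, n = 33:

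| Counts transfused | False significant rise |
|---|---|
| 0% | about 5-22% (upper end if patient means run to about 25,000) |
| 10% | 13-27% |
| 20% | 24-53% |
| 40% | 44-96% |

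At n = 15 the range is 9-62% over shares of 10-40%, and 22-62% at 40%.

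**4. Size, second model.** Log-normal counts, median 10,000 or 15,000, between-patient log SD 0.4, within-patient CV 20% or 40%, increments from 0 up to 20,000 or 40,000, n = 33:

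| Counts transfused | Wilcoxon | Paired t |
|---|---|---|
| 0% | 4-41% | 5-52% |
| 25% | 23-83% | 36-96% |
| 50% | 57-100% | 72-100% |

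With transfusion, the mean spurious rise was about 2,000-12,000/µL. The direction was upward in every setting, but in the mildest one (no transfusion, median 10,000, CV 20%) it was only about 200/µL.

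**5. Hemoglobin.** Assumed mean 88 g/L, between-patient SD 8, within-patient SD 5, +10 g/L if transfused, n = 33, paired t. With 30% transfused at both times, false rises were 3% if no patient needed hemoglobin below 100 to qualify, 5.5% if half did, and 18% if all did. If the transfused share rose from 10% to 40%, they were 43-72%.

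**6. Which scoring rule works.** Main model, no drug effect. Re-scoring only transfused follow-up counts leaves raised baselines in place: at the smaller increment it gave false falls in 16% of trials at 40% transfused and 27% at 60%. Scoring the pair as no change if either count is transfused kept false rises at 3-9% and false falls at or below 2%.

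**The case against.** The case against is substantial, and several parts of it stand.

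- **The tests are exploratory.** Protocol 10.4.2 disclaims hypotheses, relies on interval estimation and labels these tests exploratory. SAP 10.4 tabulates transfusions before treatment, before week 16 and after week 16, so readers will see transfusion use. This limits the stakes. It does not correct the p-value, because that table is not linked to the individual counts.
- **n = 33 does not describe the SAP's tests.** The SAP lists weeks 24 and 36 only, when roughly 15 patients remain, all of them responders in some lineage. This stands: the n = 15 figures are the closer guide there, and even they omit the selection of responders. The n = 33 figures apply to the week-16 test in the protocol.
- **The transfused shares and increments have no source in the plan.** True. The direction for platelets follows from the entry rule; the size does not.
- **Transfusion is not the only cause.** A reader might infer that a significant platelet rise would be due entirely to donor platelets. The documents do not support that: the entry cap alone produces regression to the mean, as the 0% rows show.
- **Hemoglobin.** A reader might also infer a firm upward bias here. The documents do not support that either, because hemoglobin below 100 g/L is not mandatory and the bias is small when transfusion use is equal at both times, unless most patients qualified through low hemoglobin.

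**Conclusion.** The point holds for platelets and, less clearly, for hemoglobin. As written, the paired platelet tests compare a capped baseline with uncapped, possibly transfused counts, so p<0.05 cannot be read as a drug effect. Under no drug effect and 10-40% of counts transfused, false rises run at about 13-96% (n = 33) or 9-62% (n = 15), and at about 5-22% with no transfusions, against 2.5%. These sizes depend on assumed variability, increments and transfusion shares; how many patients have true means near 20,000/µL matters most when there is no transfusion.

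It would be wrong to conclude that the primary result is compromised. The responder analysis does not use these tests, and its partial-response criteria for platelets and hemoglobin require transfusion independence. The harm is confined to supportive p-values.

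**What to change.** In Protocol 10.4.2 and 10.5.1 and SAP 10.2:

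1. Flag each platelet (hemoglobin) count, at baseline and at follow-up, that was preceded by a platelet (red cell) transfusion within a pre-specified window for that lineage. Use transfusion dates, not the whole interval since the previous visit. That interval is 4 weeks at weeks 16 and 24 and 6 weeks at week 36, long enough to erase a genuine rise.
2. In the paired test, score the pair as no change if either count is flagged, and report how many pairs were re-scored.
3. Show raw-count changes descriptively, without a p-value.
4. State in both documents that these tests are exploratory. State also that the <20,000 entry cap, through regression to the mean, and at weeks 24 and 36 the withdrawal of non-responders, prevent reading p<0.05 as a drug effect. No transfusion rule removes either problem.

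If the week-16 test is kept, list it in the SAP, which now omits it.

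No new collection should be needed. Transfusions are recorded at each visit, and SAP 10.4 already counts days with transfusions, which implies that dates are held. The cost is a few lines of text, the choice of two windows and one merge with the Supportive Care Record. The downside is small: a genuine responder with a transfusion inside the window is scored conservatively.

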10.4.3 Handling of missing values/censoring/discontinuations

The reason for discontinuation from study will be summarized and listed, along with dates of first and last study drug, duration of exposure to study drug and date of discontinuation for each patient.

Other missing data will be noted as missing on appropriate tables/listings.

10.4.4 Supportive analyses

Additional supportive analysis may be conducted if appropriate.

10.5 Secondary objectives

Secondary objectives are listed in [Table 3-1](#).

10.5.1 Other efficacy objective(s)

- To determine the response in each haematological lineage separately, the absolute frequency and valid percentage of patients who have a response in the neutrophil, platelet, and Hb lineages separately after 16, 24 and 36 weeks of eltrombopag, will be presented with the 95% CI. Descriptive statistics will also be provided between baseline and weeks 16, 24 and 36 for ANC, platelets and hemoglobin levels, and the appropriate paired exploratory tests will be done according to the type of distribution (parametric or not) to assess the statistical significance of the changes.
- To evaluate the overall hematological response rate (partial and complete) at 24 and 36 weeks after the initiation of eltrombopag, the frequency and percentage distribution and the corresponding 95% CI will be provided. This CI will be constructed as for the primary efficacy endpoint. Descriptive statistics will also be provided between baseline and week 24 and week 36 for ANC, platelets count and hemoglobin levels, and the appropriate paired exploratory tests will be done according to the type of distribution (parametric or not) to assess the statistical significance of the changes.
- To evaluate transfusion independence, the percentage of patients who were previously transfusion-dependent and do no longer require a RBC or platelet transfusion before and after the first 16 weeks of treatment will be calculated along with the 95% CI. This CI will be constructed as for the primary efficacy endpoint. The period where patients did not receive any platelet or RBC transfusions during the treatment period and follow-up will also be analyzed.

- To evaluate the discontinuation or reduction of concomitant G-CSF and/or EPO therapy, the percentage of patients who discontinue or reduce by $\geq 50\%$ from baseline the use of concomitant G-CSF and/or EPO therapy will be calculated along with the 95% CI. This CI will be constructed as for the primary efficacy endpoint.
- Overall survival, defined as the duration from inclusion in the study to date of death (whatever the cause), will be estimated with the Kaplan-Meier curves method and two-sided 95% CI for the estimated median. All patients who discontinue from the study, regardless the reason of discontinuation, will be followed for survival for 24 and 36 weeks, unless they withdraw their consent, die or are lost-to follow-up, in which case will be censored at the last contact.
- The overall survival rate will be evaluated by the percentage of patients still alive at 24 and 36 weeks.

